This study will systematically evaluate whether cannabinoids can enhance the analgesic efficacy of opioids, which will advance the use of cannabinoids for the treatment of acute and/or chronic pain. Chronic pain affects over 100 million Americans. Opioids are unanimously recognized as the most effective drugs for the relief of pain and suffering, but the US is now suffering from an epidemic of abuse, addiction and accidental deaths resulting from the increased sale and use of opioids. There is legitimate value in identifying adjuncts that might reduce reliance on opioids while maintaining adequate pain relief. Preclinical studies report that co-administering cannabinoids with opioid agonists significantly and reliably reduce the amount of opioids required for analgesia but this hypothesis has not been rigorously evaluated in humans. This proposal will evaluate the effect of dronabinol on opioid-induced analgesia. The study will enroll 60 healthy adults (30 men/women) to conduct a within-subject, dose-response evaluation of cannabinoids on the analgesic effect of hydromorphone (Dilaudid). Subjects will complete 5 experimental sessions that will occur at least once weekly and will enable subjects to admit themselves into a clinical research unit the night before the session to complete the study session. Subjects will receive a dose of hydromorphone (4mg, oral) and a double-blind oral dose of study drug or placebo the morning of each experimental session, and will undergo quantitative sensory testing (QST; a comprehensive pain testing battery), provide self-report ratings of drug effects, and complete a neurocognitive battery. QST testing will comprehensively and systematically measure pain sensitivity, and provide information on the full range of analgesic effects possible across a wide variety of pain measures, including threshold responses (thermal, pressure), temporal summation, cold pressor, conditioned pain modulation, and capsaicin sensitization. Primary outcomes will be magnitude and duration of pain as a function of study drug dose. Additional primary aims include proxy measures of abuse liability and neurocognitive performance. All measures will be assessed as a function of sex, due to substantial evidence that men/women differ with regard to pain perception, endogenous cannabinoid receptor density, and opioid response. We hypothesize that cannabinoids will shift the analgesic curve of hydromorphone and enhance analgesia effects. This will be the 1st human laboratory study to evaluate combinations of cannabinoids and opioids using QST, and results will identify whether a signal for this medication combination exists that should be advanced into randomized controlled trial evaluations with clinical pain populations. This study will also assess aspects that would impact drug development (abuse liability, neurocognitive impairment), as well as the effects of sex and cannabinoid type on outcomes. Results from this study will help advance the acceptance of cannabinoids from use with only treatment-

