
refractory pain conditions to widespread societal use for clinical pain.

2. **Objectives** (include all primary and secondary objectives)
 1. **Primary Aim 1: Evaluate the magnitude and duration of combined dronabinol and hydromorphone to reduce pain sensitivity in a validated model of pain.** We hypothesize that the addition of a dronabinol to hydromorphone will result in a dose-dependent increase in the magnitude and duration of analgesia in patients undergoing a validated laboratory model of pain.
 2. **Primary Aim 2: Evaluate the subjective responses to combinations of dronabinol and hydromorphone to determine the subjective, euphoric effects of the combination products.** We hypothesize that dronabinol will not increase the subjective ratings of positive drug effects or other proxy measures of abuse liability, relative to hydromorphone alone.
 3. **Primary Aim 3: Evaluate the degree to which combining dronabinol with hydromorphone impacts neurocognitive performance.** We hypothesize that dronabinol may reduce neurocognitive performance at high doses, relative to hydromorphone alone, though the degree to which this may occur is unknown. This aim is critical for the advancement of potential opioid/cannabinoid combination products.
 4. **Secondary Aim 1: Evaluate whether there are sex differences on study outcomes.** We hypothesize that dronabinol enhancement of hydromorphone-analgesia will be greater among female vs. male subjects.
3. **Background** (briefly describe pre-clinical and clinical data, current experience with procedures, drug or device, and any other relevant information to justify the research).

This study will systematically evaluate whether cannabinoids can enhance the analgesic efficacy of opioids, which will advance the use of cannabinoids for the treatment of acute and/or chronic pain.

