The morning of each experimental session, the subject will receive a calorie-controlled breakfast each morning. Following breakfast, subjects will complete a baseline rating of QST and self-report measures (from which all subsequent ratings will be compared for data analysis purposes). An oral capsule containing either study drug or placebo will then be administered and hydromorphone (4mg oral in four sessions and a placebo oral dose in one session) will be administered. The time of drug administration will be selected to enable both dronabinol and hydromorphone to exert peak effects at the same time. Subjects will complete QST (see below) and self-report measures at regular intervals following study drug administration. Self-report measures will include specific opioid agonist and antagonist effects, to assess whether cannabinoids are exerting an effect on a particular category of opioid agonist symptom, and will capture whether any negative effects (e.g., nausea) occur as a function of the cannabinoid dose. Frequent collection will enable evaluation of time to peak drug effects, duration of effects, and general time course of effects and is a widely used and accepted approach in laboratory studies of drug effects. During the final assessment each day, subjects will complete a Drug vs. Money Questionnaire to indicate the dollar value they would place upon the drugs received⁹⁸. This is a well-accepted proxy measure of abuse liability. Study staff will document adverse events throughout the study and any subject who experiences a strongly unpleasant effect of the medications will be able to end participation. Any subject who is experiencing strong agonist effects at the end of the session will be provided overnight accommodation in the CRU; based on our experience we expect this to be minimal and are budgeting for 10% of sessions to have a 2nd night.

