Dronabinol (Marinol) has been strategically chosen for this study because it is a widely-used, commercially-available Schedule II cannabinoid medication that is currently indicated for nausea and vomiting, and anorexia in AIDS patients, **but which could be prescribed off-label for the adjunctive treatment of clinical pain.** Dronabinol is a synthetic delta-9-tetrahydrocannabinol (THC) product (the primary psychoactive compound in cannabis sativa (marijuana)), and thus has generality with other THC compounds (such as smoked or edible marijuana products). When administered orally (as proposed here), dronabinol reaches peak concentrations in 2-4 hours and is 90-95% absorbed but, due to extensive first-pass metabolism, is only 10-20% bioavailable. It is excreted in fecal (35-50%) and renal (10-15%) waste. The elimination half-life is biphasic, with an initial half-life of 4 hours and a terminal half-life of 25-36 hours, and an active metabolite (11-hydroxy-delta-9-THC) is produced. There is no current evidence that dronabinol is differentially affected by P450 status. Dronabinol is sold commercially in 2.5mg, 5mg, and 10mg dose ranges. **We have chosen to administer a 0 mg (placebo), 2.5mg, 5mg, and 10mg, dose of dronabinol in this study,** which are within the range currently prescribed for chemotherapy-induced nausea and vomiting and AIDS-

related anorexia, and therefore will have direct clinical applicability. Dronabinol will be purchased as a capsule and will be over-encapsulated by our research pharmacy to ensure double-blind administration procedures. Placebo doses will consist of lactose or another benign weight-matched filler.

- b. Justification and safety information if FDA approved drugs will be administered for non-FDA approved indications or if doses or routes of administration or participant populations are changed.

Hydromorphone: Hydromorphone hydrochloride is a pure mu opioid agonist that can be administered in oral, rectal, intramuscular (IM) or intravenous (IV) formulations for the indication of acute and/or chronic pain.

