- **Primary Aim 1:** The primary outcome will be the area under the curve of each QST procedure, which will provide an assessment of the mean duration and magnitude of the drug effect. Primary outcomes will be tested with repeated two-factor (Drug Condition x Time) models to examine main and interaction effects for all raw data as designed. If there is large variation across subjects at the baseline timepoint, the raw data will be transformed as a change from baseline and analyzed in drug condition by time models. Statistical analyses will be conducted using multilevel analyses with an autoregressive covariance structure using SAS PROC MIXED Software¹³¹. These analyses will permit an examination for effects of drug condition and time effects associated within the course of the study. Interpretation of drug condition main effects and interactions will rely on Tukey post-hoc tests. This aim will also assess frequency of adverse events as a function of study drug.

Specific outcome variables for the QST procedures will be as follows:

- a. Heat Pain Threshold and Tolerance: HPT_h and HPT_o in °C (both in normal and capsaicin treated skin)
 - b. Pressure Pain Threshold: PPT_h in kilopascals
 - c. Thermal and Mechanical Temporal Summation: Verbal pain ratings (both in normal and capsaicin treated skin for MTS)
 - d. Conditioned Pain Modulation: The index score of CPM:PPT_h and CPM:TS (compared to baseline) for each dose
 - e. Cold Water Tolerance: Time to tolerance (compared to baseline) for each dose.
- **Primary Aim 2:** The Drug vs. Money questionnaire will be compared across dose conditions, using peak monetary rating for each dose as the primary outcome. Within-subject changes, as a function of dose, will be analyzed using a repeated measures analysis of variance (ANOVA).
 - **Primary Aim 3:** Neurocognitive tests will be compared as a function of study drug dose, using study session number (1-6) as a covariate to control for practice effects. Specific outcome measures will include:
 - a. Divided Attention Task (DAT): Accuracy with which they perform the two tasks
 - b. Digit Symbol Substitution Task (DSST): Accuracy, total number of patterns completed in allotted time
 - c. Computerized version of the Paced Auditory Serial Addition Task (PASAT): Summed of correct trials

b. Secondary outcome variables.

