The most serious potential adverse event following hydromorphone administration is opioid agonist overdose, which is characterized by respiratory depression, somnolence progressing to stupor or coma, skeletal muscle flaccidity, cold and clammy skin, constricted pupils, and sometimes bradycardia and hypotension. In serious overdosage, particularly following intravenous injection, apnea, circulatory collapse, cardiac arrest and death may occur. We believe the risk of overdose in this study to be low for the following reasons: we have extensive experience in the administration of hydromorphone, we have chosen doses that have been demonstrated to be safe and tolerable in an identical participant population, we will exclude any individual who has a medical condition that

may increase the risk for respiratory depression and/or other adverse events, all medication doses will be administered by a trained research nurse, and participants will be monitored throughout the study session, up to 8 hours, by trained staff who will have access to the opioid antagonist naloxone to reverse the opioid agonist effects. Hydromorphone has no known interactions with dronabinol.

b. Dronabinol: The FDA identifies the following adverse effects of dronabinol: cardiovascular (hypertension, hypotension, palpitations, tacharrhythmia, vasodilation); dermatologic (flushing); gastrointestinal (abdominal pain, nausea, vomiting, xerostomia); neurological (amnesia, ataxia, confusion, coordination problem, dizziness, somnolence, vertigo), and psychiatric (anxiety, delusion of persecution, depersonalization, depression, disturbance in thinking, euphoria, hallucinations), though it should be noted that the adverse effects were collected from studies of patients undergoing chemo therapy or with advanced HIV, which may have decreased their threshold for experiencing negative effects. Dronabinol is listed as pregnancy category C, meaning that preclinical studies have revealed adverse effects on the fetus but that no controlled human studies have been conducted to assess this risk (pregnancy or breast-feeding will be an exclusion criterion). The only absolute contraindication of dronabinol is allergy or hypersensitivity to cannabinoids or sesame oil. Dronabinol has moderate – severe interactions with breast cancer resistance protein inhibitors (topotecan, ataluren), and has moderate interactions with the antiretroviral protease inhibitor ritonavir (Norvar), which is used to treat HIV and AIDS.

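### Primary Aim 1 targets both magnitude and duration of analgesia, but its AUC outcome cannot separate them, no duration outcome is defined, and sections 7.a and 7.c name different primary outcomes

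*Combined protocol and SAP*

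**What the plan says.** The opening summary of the protocol states: "Primary outcomes will be magnitude and duration of pain as a function of study drug dose". Section 2 (Primary Aim 1) hypothesises a "dose-dependent increase in the magnitude and duration of analgesia". Magnitude and duration are thus both targets of the aim.

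Section 7.a (Primary Aim 1) then specifies: "The primary outcome will be the area under the curve of each QST procedure". The reason it gives for this choice is that the summary is one "which will provide an assessment of the mean duration and magnitude of the drug effect". On the analysis it says: "Primary outcomes will be tested with repeated two-factor (Drug Condition x Time) models to examine main and interaction effects". Tukey tests follow. The outcome list beneath gives the unit or score for each QST measure, but no peak or duration summary.

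Section 7.c bases the sample size on a different outcome. It treats peak change from baseline as the primary outcome measure, with 6 conditions, effect size 0.2, power 0.95 and 45 participants.

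On timing, section 4.a says only that QST is repeated at regular intervals after dosing. It gives no hours, no last battery and no AUC limits. It expects frequent collection to allow time to peak, duration and time course to be evaluated, but defines no variable for any of them. The only session length is in the hydromorphone risk text of section 8.a: "participants will be monitored throughout the study session, up to 8 hours". Section 6.a puts the dronabinol peak at 2-4 hours and describes a biphasic decline, "with an initial half-life of 4 hours and a terminal half-life of 25-36 hours". Sections 4.a and 6.b give a half-life of 19-36 hours.

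**The concern.** An AUC is a composite of height and length. If it rises with dronabinol dose, the plan as worded invites the conclusion that analgesia was both stronger and longer, when only one may have changed. The two have different clinical meanings, and the aim names both.

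The specification also does not hold together. One AUC per session has no time factor, so it cannot be the response in a Drug Condition x Time model. The stated power belongs to yet another summary, peak change. If the definitions of peak, duration and window are left until the curves have been seen, across many QST measures, the choice among them is open to selective reporting.

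**Working it through.** **1. The plan's own figure.** Section 7.c gives effect size f = 0.2, m = 6 conditions, power 0.95 and N = 45. Assumed because not stated: alpha 0.05, correlation between conditions rho = 0.5, sphericity.

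- Noncentrality = f² x N x m / (1 - rho) = 0.04 x 45 x 6 / 0.5 = 21.6, with df = 5 and 44 x 5 = 220.
- Power at N = 45 is 0.962, and the smallest N for 0.95 is 43. The stated figure reproduces.
- It depends on rho: the smallest N is 59 at rho 0.3, 51 at 0.4 and 35 at 0.6.
- The dosing table in section 6.a lists five conditions. With m = 5 and rho 0.5, power at 45 is 0.937 and the smallest N is 48.

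The calculation was made for peak change. The documents give neither an effect size nor a correlation for AUC, so it does not show the power for the outcome named in section 7.a.

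**2. What an AUC can separate.** Two illustrative effect profiles, hourly from 0 to 8, by the trapezoid rule:

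| Hour | 0 | 1 | 2 | 3 | 4 | 5 | 6 | 7 | 8 | AUC | Peak | Points at or above 5 |
|---|---|---|---|---|---|---|---|---|---|---|---|---|
| A | 0 | 10 | 20 | 20 | 10 | 0 | 0 | 0 | 0 | 60 | 20 | 4 |
| B | 0 | 5 | 10 | 10 | 10 | 10 | 10 | 5 | 0 | 60 | 10 | 7 |

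Both profiles start and end at 0, so each AUC is the sum of its hourly values: A is 10 + 20 + 20 + 10 = 60, and B is 5 + 5 x 10 + 5 = 60. One is twice as high and the other lasts longer, and the AUC is identical.

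**3. What the Drug Condition x Time model adds.** The differences A - B at hours 1 to 7 are +5, +10, +10, 0, -10, -10 and -5. An interaction test on the repeated values could detect this pattern. It would show that the curves differ in shape, but would not yield a time for which analgesia lasts or a contrast of such times between doses.

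**4. Why the window matters.** If the last battery were at hour 6, A would still give 60, but B would give 5 + 10 + 10 + 10 + 10 + (10/2) = 50 and would still be at 10 when observation stopped. The AUC comparison changes with the cut-off, and the end of B's effect is not seen. The protocol does not state the cut-off.

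**5. How likely is a cut-off effect?** Fraction of peak dronabinol remaining at time T = 0.5^((T - peak time) / half-life), assuming one-phase decay and ignoring the active metabolite:

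- T = 8 h, half-life 4 h: 0.5^(6/4) = 0.35 (peak at 2 h) to 0.5^(4/4) = 0.50 (peak at 4 h).
- T = 8 h, half-life 19-36 h: 0.5^(6/19) = 0.80 to 0.5^(4/36) = 0.93.
- T = 7 h, if about an hour of the session precedes dosing (assumption), half-life 4 h: 0.5^(5/4) = 0.42 to 0.5^(3/4) = 0.59.

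Under every half-life in the documents, a substantial share of drug is present at 8 hours. These are concentrations, not analgesia.

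**The case against.** The strongest defence is that the plan is richer than one AUC. The models are fitted to the repeated raw data with interactions and Tukey tests, so time-specific contrasts can show whether conditions differ near the peak and late in the session. Section 7.c names a peak outcome, and section 4.a states the intention to examine duration. This stands in part: the data will carry information on both features, and it would be wrong to say that AUC is the only outcome named or that nothing could be learned about duration. It does not remove the gap, because no duration variable, margin or rule for continuing effects is defined, and the peak outcome appears only in a power statement that contradicts section 7.a.

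A reader might also infer that the AUC is truncated at 8 hours, that this affects about 10% of sessions, and that prolongation is therefore understated most at the higher doses. The documents do not support this chain:

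- The 8 hours is a safety-monitoring maximum, not a QST window. Section 8.b elsewhere speaks of 24-hour monitoring.
- Section 4.a says "Any subject who is experiencing strong agonist effects at the end of the session will be provided overnight accommodation in the CRU", but this concerns agonist effects in general, not QST responses. The 10% is a budget for second nights that the protocol expects to be minimal.
- Residual drug is not residual analgesia. The documents give no effect-time data, and section 8.a describes hydromorphone side effects as generally gone within several hours.
- Greater truncation at higher doses is plausible but not shown.

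**Conclusion.** The point holds on the specification of the outcome and needs no pharmacokinetics. Magnitude and duration are both targets of Primary Aim 1. The AUC in section 7.a cannot attribute a difference to either, the planned models do not estimate duration, and no duration outcome is defined. Sections 7.a and 7.c name different primary outcomes and must be reconciled. The AUC remains usable as an overall measure of effect, but as written a positive AUC would not support the two-part claim.

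Censoring of duration is a risk only. Its size cannot be stated, because battery times and AUC limits are missing. The 35% to 50% of peak drug at 8 hours assumes that the monitoring maximum is the window, the 4-hour half-life and one-phase decay. The equal-AUC profiles are illustrative, not predictions.

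**What to change.** Amend section 7, before unblinding:

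1. State which of AUC and peak change is primary, make sections 7.a and 7.c agree, and restate power for that outcome with the number of conditions, correlation and alpha shown.
2. State the QST battery times, and define the AUC as running from dosing to the last scheduled battery.
3. Define peak change from pre-dose baseline, in the analgesic direction for each measure, as the basis for any claim about magnitude.
4. Define a duration measure as the basis for any claim about duration. An example is restricted mean time from dosing until return to within a pre-stated margin of baseline, censored at the last battery and set to zero for a measure that never leaves the margin. Otherwise drop the separate duration claim.
5. State the order of these outcomes and how multiplicity across QST measures is handled. The Tukey tests compare conditions and do not address the number of measures. An outcome on which a primary claim rests should not rank below one that cannot support that claim.

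The cost is section 7 wording and modest extra analysis, with no new visits or measurements. The downside is two more summaries per QST measure. Section 7.a lists about 11: four heat, one pressure, three temporal summation, two conditioned pain modulation and one cold tolerance. That makes about 2 x 11 = 22 further summaries, which is why the order and multiplicity rule belong in the same amendment.

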Quantitative Sensory Testing (QST) Measures of Laboratory Evoked Pain: Subjects will complete a state-of-the-art quantitative sensory testing (QST) battery, which will comprehensively and systematically measure pain sensitivity. This approach will provide information regarding the full range of analgesic effects possible, across a wide variety of psycho-physiologically-mediated, experimentally-induced measures of pain perception. Subjects will complete a baseline QST session prior to study drug administration on each experimental session day, and will complete the pain testing battery at regular intervals during the experimental session day. Each administration of the QST battery will take 20-30 minutes. The QST battery will consist of threshold and tolerance, temporal summation, and conditioned

pain modulation (CPM) tests. The threshold responses will be conducted in randomized and counter-balanced order, and conditioned pain modulation will always occur last.

Threshold Responses will be assessed using thermal and pressure stimulation. *Thermal threshold:* All contact heat stimuli will be delivered using a peltier-element-based stimulator (Medoc, Israel). Two trials of heat pain threshold will be administered using an ascending method of limits paradigm. The thermode will gradually increase in temperature (rate of rise = .5°C/sec) from a pre-set baseline (31°C), until the subject indicates when the stimulus “first feels painful” (threshold, HPT_h) and presses a button (which terminates the procedure) indicating that the pain is intolerable (tolerance, HPT_o). *Pressure threshold:* A pressure algometer will be utilized to assess responses to pressure stimulation at a variety of anatomical sites in a randomly determined order. The pressure algometer (Somedic; Sweden) uses a rubber probe covered with 1mm polypropylene material; pressure at the site is gradually increased at a steady rate. Subjects indicate when the stimulus is first perceived as painful, which terminates the application. The algometer produces a sensation of localized pressure; technicians will place the probe of the algometer in the center of each muscle group or anatomic site when delivering the mechanical stimuli. Thirty-second inter-stimulus intervals will be maintained for all stimuli. Each trial will be averaged together to result in one HPT_h, HPT_o, and PPT_h measure.

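### On its natural reading, the default Aim 1 model makes the pre-dose value a level of Time, which dilutes the condition main effect and leaves baseline adjustment to a switch with no threshold

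*Combined protocol and SAP*

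**What the plan says.** Section 7.a, Primary Aim 1, states: "The primary outcome will be the area under the curve of each QST procedure". The test is by "repeated two-factor (Drug Condition x Time) models to examine main and interaction effects for all raw data as designed", fitted as "multilevel analyses with an autoregressive covariance structure using SAS PROC MIXED Software". The following provision reads: "If there is large variation across subjects at the baseline timepoint, the raw data will be transformed as a change from baseline". No threshold for a large variation is given. On reporting, the section says: "Interpretation of drug condition main effects and interactions will rely on Tukey post-hoc tests".

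In the list of outcome variables, the conditioned pain modulation (CPM) index and cold water tolerance are defined relative to baseline; the second, for example, is "Time to tolerance (compared to baseline) for each dose". Heat pain, pressure pain and temporal summation carry no such reference. No baseline covariate is named for any Aim 1 model.

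Section 4.a (QST Measures) states: "Subjects will complete a baseline QST session prior to study drug administration on each experimental session day". Section 4.a (Experimental Sessions) describes that baseline as the value "from which all subsequent ratings will be compared for data analysis purposes". Section 7.c bases the sample size on peak change from baseline. The number and timing of post-dose batteries are not given.

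**The concern.** A value taken before dosing cannot carry a drug effect. If it is one of the levels of Time, the condition main effect averages a point of zero expected drug effect with the post-dose points, so the reported effect is smaller than the one of interest. On the raw scale the main effect also leaves in the session-to-session variation within a person, which the same-day baseline could partly remove.

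The section does provide for change from baseline, but only after the data have been inspected, without a stated limit, and on a criterion (spread across subjects) that largely cancels when each person is compared with himself or herself. A raw default also sits poorly with section 4.a, where every rating is to be compared with baseline, and with section 7.c, where power is for a change score. At stake are the size and precision of the Aim 1 condition effect, mainly for heat, pressure and temporal summation.

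**Working it through.** **1. The plan's own power figure.** Section 7.c gives power 0.95 for 6 conditions, effect size f = 0.2 and N = 45. Assume alpha 0.05, correlation 0.5 and sphericity, none of which is stated. The noncentrality is f²·N·m/(1−ρ) = 0.04 × 45 × 6/0.5 = 21.6, with 5 and 220 degrees of freedom. Power is 0.962, and 43 participants suffice for 0.95, so the figure reproduces. With the 5 sessions in the design, noncentrality is 18.0 and power 0.937. Either way the figure is for peak change from baseline and does not describe a raw-data main effect.

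**2. Dilution of the main effect.** With complete data the main effect weights the Time levels equally, whatever the covariance structure. One pre-dose level plus T post-dose levels gives (0 + T × mean post-dose effect)/(T+1), a factor of T/(T+1). For an equally spaced trapezoidal AUC starting at baseline, the baseline has weight 1/(2T), so a constant post-dose effect is multiplied by 1 − 1/(2T).

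| T (assumed) | Main effect | Trapezoidal AUC with baseline |
|---|---|---|
| 4 | 0.80 | 0.875 |
| 6 | 0.86 | 0.917 |
| 8 | 0.89 | 0.9375 |

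A post-dose or baseline-corrected AUC has no such dilution.

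**3. Precision.** Remove the participant effect and set the variance of one assessment to 1. Let Vp be the variance of the session's post-dose mean and c its covariance with the baseline.

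- Raw, post-dose only: Vp.
- Raw, baseline included, rescaled to the post-dose effect: Va = Var(mean of T+1 values) × ((T+1)/T)².
- Change from baseline: Vp + 1 − 2c.
- Post-dose with baseline covariate: Vp − c².

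For AR(1) with lag-1 correlation ρ, Vp = [T + 2Σ(T−k)ρᵏ]/T² for k = 1 to T−1, and c = (Σρᵏ)/T for k = 1 to T. For constant correlation r, Vp = [1 + (T−1)r]/T and c = r.

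Example, AR(1), ρ = 0.5, T = 4:
- Vp = (4 + 2 × 2.125)/16 = 0.516
- Va = (5 + 2 × 3.0625)/25 × 1.5625 = 0.695
- c = 0.9375/4 = 0.234
- adjusted variance = 0.516 − 0.055 = 0.461

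Including baseline costs 0.695/0.516 = 1.35 times the participants. Leaving out the covariate costs 0.516/0.461 = 1.12 times. The total is 1.51.

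| Within-session correlation (assumed) | T | Baseline included v post-dose only | No covariate v covariate | Total |
|---|---|---|---|---|
| AR(1), 0.2 | 4 / 8 | 1.28 / 1.13 | 1.01 / 1.01 | 1.29 / 1.14 |
| AR(1), 0.5 | 4 / 8 | 1.35 / 1.15 | 1.12 / 1.05 | 1.51 / 1.21 |
| AR(1), 0.8 | 4 / 8 | 1.46 / 1.20 | 1.82 / 1.40 | 2.66 / 1.68 |
| AR(1), 0.9 | 4 / 8 | 1.51 / 1.23 | 3.12 / 2.13 | 4.71 / 2.62 |
| Constant, 0.2 | 4 / 8 | 1.41 / 1.22 | 1.11 / 1.15 | 1.56 / 1.41 |
| Constant, 0.5 | 4 / 8 | 1.50 / 1.25 | 1.67 / 1.80 | 2.50 / 2.25 |

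As an illustration for a single two-sided 5% contrast where the adjusted model has 80% power, the raw model has Φ(2.80/√total − 1.96). That is about 75% at a total of 1.14 and 25% at 4.71.

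**4. The switch.** Change scores improve on raw post-dose data only when 1 − 2c < 0, that is c > 0.5. Adjustment is never worse than either: it is c² below raw post-dose and (1 − c)² below change. Variance between participants appears in none of these expressions, provided the model carries a participant effect. The plan calls the model multilevel but does not list its random terms.

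**The case against.** The strongest reply is that the plan does use the session baseline, so it would be wrong to infer that it does nothing to reduce error.

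- With baseline as a level of Time, the Condition x Time interaction contrasts post-dose values with the same day's baseline and removes a constant session shift. At T = 4 and constant correlation 0.5 that contrast has variance 0.625, against 0.938 for the raw main effect. At correlation 0.2 it is worse (1.000 against 0.562). Tukey tests on the interaction are not diluted.
- The switch to change scores may well be triggered for some measures. Section 4.a itself gives capsaicin pain as 48.25 ± 27.93.
- CPM and cold water tolerance are already referred to baseline.

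It can also be said that no sentence states that Time includes the pre-dose value, and that sections 4.a and 7.c point towards change from baseline. The T/(T+1) factor does not carry over to AUC, the named primary outcome. The constant-correlation figures use a structure that the plan does not specify.

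All of this stands as a limit on the point. It does not remove the dilution of the main effect on the natural reading, the absence of a baseline covariate, or the lack of a threshold for the switch.

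**Conclusion.** The point holds in limited form. If baseline is a level of Time, as the wording most naturally implies, the condition main effect is 80% to 89% of the mean post-dose effect for T = 4 to 8, or 87.5% to 94% for a trapezoidal AUC that includes baseline. Under the AR(1) correlations tried (0.2 to 0.9), including baseline costs about 1.1 to 1.5 times the participants. The further loss from not adjusting is 1% to 12% at correlations of 0.2 to 0.5 and reaches a factor of about 3 at 0.9. T and the correlations are assumptions, so the power figures are illustrations and not properties of this trial.

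A reader might infer that the Aim 1 test is invalid. The documents do not support that: under no drug effect the diluted contrast is still zero, and type I error is not raised. Nor do they support the claim that the plan definitely fixes a diluted model; sections 4.a, 7.a and 7.c pull in different directions and need to be reconciled. This should be corrected, as an avoidable loss on a primary aim.

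**What to change.** In section 7.a:

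1. Use post-dose assessments only as the response, or define a post-dose AUC, and state the assessment times.
2. Include the session's pre-dose value as a prespecified covariate in the Aim 1 models. Entering the participant's mean baseline plus the session's deviation from it is one sound choice among several.
3. Estimate the condition effect over post-dose times.
4. Remove the raw-data default and the data-driven switch to change scores.

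Sections 4.a and 7.c should then refer to the same response. The cost is SAP wording and one or two model degrees of freedom; the baseline is already collected in every session.
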